6.4 Statistical Method

6.4.1 Statistical Design

Baseline demographic and clinical characteristics will be tabulated for the overall study cohort as well as stratified by randomized treatment assignment. Baseline characteristics will be assessed for association with the primary study abstinence outcomes using univariable logistic regression models and resulting effect sizes will be reported. The primary purpose to this pilot trial is to ascertain study efficacy and determine effect sizes of varenicline on vaping abstinence. End of treatment and study follow up 7-day point prevalence abstinence rates will be tabulated and compared between varenicline, and placebo treated participants using a modified Poisson regression approach. Proportion abstinent as well as risk ratios and associated 95% confidence intervals will be provided for the entire study time course as well as stratified by study time point (end of treatment, study follow-up). Initial models will be adjusted for baseline vaping behavior as well as strata utilized in the randomization procedure. Sensitivity analysis will be employed to compare results from available study data to those with missing study data imputed to vaping (single imputation to worst case outcome). Study results will be utilized to design and sufficiently power a follow up RCT.

Secondary analysis of average reported vaping puffs per day and vaping days per week will be examined using generalized linear mixed effects models (GLMMs). Vaping puffs will be summarized weekly and differences between randomized treatment groups will be assessed during the treatment and follow up time periods. Model based means and standard errors will be used to determine pairwise comparisons and meaningful time points (weeks 8 and

12). The number vaping days per week will be assessed using GLMMs with a negative binomial specified distribution for count data. Median (inner quartile range) vaping days as well as risk ratios and associated 95% confidence intervals will be provided. Longitudinal models will include study treatment, week, and the associated interaction when appropriate.

6.4.2 Safety

Adverse events will be collected for all study emergent events throughout the treatment phase of the study. The proportion of participants reporting study emergent adverse events will be compared between groups using a Chi-Square test (Fisher's exact test when appropriate).

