3.2.1 Potential Risks

The main study procedures include completion of questionnaires (minimal risk), varenicline use (use will be tracked as well as any new or recurring symptoms), and Truth Initiative texting services. This is a low-risk medication study (see text below). There is also a risk that the treatment the study participant is randomized to may prove to be less effective than the other study treatment or other available treatments (i.e., participants who receive placebo). We will conduct scheduled assessment throughout the intervention to review participant symptoms, mood, and wellbeing.

Breach of confidentiality: Study investigators across both sites have experience as an investigator dealing with such sensitive information and has experience assuring that data is adequately protected. Safeguards to protect confidentiality include locked records and firewalls around password-protected electronic data, and all study data being coded, with the key linking the code with a subject's identity being kept in a separate, locked file.

Assessments and Rating Scales: All assessments and rating scales are non-invasive and involve minimal risk to study participants.

Varenicline is an FDA approved smoking cessation medication. Black-box warnings were removed by the FDA in recent years following the large clinical EAGLES trial showing that this is a low risk medication.¹ Additionally, meta-analyses have been conducted that show varenicline as a safe and useful medication.¹⁷⁻²⁰ Some side effects of varenicline include nausea, constipation, indigestion, abdominal pain, heartburn, increased or decreased appetite, trouble falling asleep or staying asleep, unusual dreams or nightmares, headache, lack of energy, back, joint, or muscle pain, and abnormal menstrual cycles.

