A novel alert system will be built into the Adverse Event surveys REDCap database such that any severe adverse events (e.g., severe nausea, severe sleep disturbances, severe changes in mood) that are endorsed along with self-report of cessation of pharmacotherapy use will be monitored by research staff, who will consult with the study physician/APRN from the Tobacco Treatment Service/PI [name] when indicated for clinical assessment and management. We believe this alert system will improve varenicline medication adherence if the pharmacist/APRN/physician can quickly follow-up on any side effects that may be associated with pharmacotherapy use and call the patient with any recommended dose adjustments. All dose adjustments will be recorded in our REDCap database.

Guided Self-Change Pamphlet: All groups will receive this pamphlet as a brief behavioral component of the intervention. This 3-page pamphlet includes information on how to reduce and quit e-cigarettes on their own (on Page 1), how to prevent relapse to combustible cigarettes (for mono vapers who quit combustible cigarettes by vaping; on Page 2), and how to enroll in the online This is Quitting services (described above; on Page 3).

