5.3.1 Number of Participants

We plan to enroll 40 participants across two sites. As with previous studies, we will make every effort to maximize participant retention via a thorough informed consent process, careful screening, and other practices.

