Weekly Electronic Assessments: Participants will be asked to complete a brief compensated assessment to assess e-cigarette use, use of other tobacco products including cigarettes, and daily medication adherence. These Assessments be completed weekly throughout the entirety of the study. Assessments will assess vaping sessions/puffs per day, use of other tobacco products, medications/products used, purposes of that use (to reduce/quit), next-

day e-cigarette use/other tobacco use/quit intentions, and mood/affect. The assessment will also assess e-cigarette brand, concentration, and habits surrounding e-cigarette use (i.e., location, type of device, and flavor choice). Weekly abstinence will be assessed in three different ways: "Have you quit today?", "Have you used an e-cigarette in the past three days?", and "Have you used an e-cigarette in the past 7 days?" To track medication adherence, the assessment will also ask how many varenicline pills that participant took per day. This will not replace traditional adverse event assessment (below) but complement (and enrich) them. We have established procedures to auto-send an email or SMS text (their choice) on a set schedule. SMS text messaging is possible via Twilio, embedded within our REDCap system, which allows participants to complete a survey directly from their phone, without having to access a webpage. Note that assessments are not completed via texting, just prompted via text with link to REDCap. Participants can choose to receive their assessment invitations via email if they wish, again with a link to a secure REDCap survey. Thus, per eligibility criteria above, we require participants to have smartphone or other device that has internet capacity. Assessments consist of a brief (<2 minutes) survey, directly enter an online protected database (REDCap) through secure encryption; all PHI is protected. Participants will be compensated for compliance based on % assessments completed (described below).

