6.3.5 On Study Visits

Assessments	Week 0	Week 4	Week 8	Week 12	Weekly
Demographics	X				
Smoking/Tobacco Use History	X				
Modified Questionnaire on Smoking Urges (QSU)	X		X	X	
E-Cigarette Dependence	X		X		
E-Cigarette Dependence Index	X		X		
Subjective Effects Cigarettes and E-cigarettes	X	X	X		
Patient Health Questionnaire-9 (PHQ9)	X				X*
Wisconsin Withdrawal Scale Brief (WSWS2-B)					
Weekly Electronic Assessments					X
Exit Survey				X	

*bi-weekly

- Baseline (Week 0):
 - Assessment
 - Randomization
- Week 1:
 - Participant sent 1 week supply of 0.5mg and 3-week supply of 1mgOrientation call about medication
 - Weekly assessments
- Week 2
 - Weekly assessments
- Week 3:
 - Weekly assessments
- Week 4:
 - Participant sent second shipment of a 4-week supply of the 1 mg dose.
 - Weekly assessments
- Week 5:
 - Weekly assessments
- Week 6
 - Weekly assessments
- Week 7
 - Weekly assessments
- Week 8
 - Weekly assessments
 - End of treatment phase
- Week 9:
 - Weekly assessments
- Week 10

- Weekly assessments
- Week 11
 - Weekly assessments
- Week 12
 - Weekly assessments
 - Exit survey

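### Section 6.4.2 compares study emergent adverse events without defining the term and without a symptom checklist before the first dose

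*Combined protocol and SAP*

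**What the plan says.** The safety analysis in Section 6.4.2 has two sentences. The first sets the collection window: "Adverse events will be collected for all study emergent events throughout the treatment phase of the study". The second sets the comparison: "The proportion of participants reporting study emergent adverse events will be compared between groups", by chi-square or Fisher's exact test. Study emergent is not defined there or elsewhere.

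Adverse event capture is described in several places:

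- Section 6.2.3 has participants rate events as mild, moderate or severe in the weekly assessments, and also lets them phone the investigators. Staff track relatedness to study medication, but formal attribution codes apply only from grade 3 upward.
- Section 6.3 (participant compensation) starts the weekly assessments at Week 1.
- Section 6.2.1 lists the content of the weekly survey without naming any adverse event item, and adds: "This will not replace traditional adverse event assessment (below) but complement (and enrich) them".
- Section 5.1 refers to a separately named instrument: "A novel alert system will be built into the Adverse Event surveys REDCap database".
- The Section 6.3.5 table has a row for the weekly electronic assessments but none named for adverse events.

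On intent, Section 3.2.1 says of varenicline that "use will be tracked as well as any new or recurring symptoms".

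The Week 0 measures in Sections 6.2.1 and 6.3.5 are demographics, tobacco history, smoking urges, two e-cigarette dependence measures, subjective effects and the PHQ-9. The row "Wisconsin Withdrawal Scale Brief (WSWS2-B)" in Section 6.3.5 is empty, and Section 6.2.1 gives that scale no week.

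**The concern.** To call an event emergent, one must know whether the symptom was there before the first dose. Several side effects listed in Section 3.2.1 (sleep trouble, headache, low energy, appetite change) are ordinary complaints that some participants may have at entry. Without the same questions before dosing, and without a counting rule, a participant who enters with headaches and ticks headache in Week 2 may be counted as having an emergent event. The stated aim of tracking both new and recurring symptoms needs the same baseline.

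What is at stake is the descriptive safety result: the event rate in each arm and the difference between them. These figures also feed the by-arm review of adverse event frequency and the annual report in Section 7.11, which asks whether rates match pre-study assumptions. The PHQ-9 and medical history can be re-read later, but a pre-dose rating of common symptoms that was never taken cannot be recovered.

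**Working it through.** **Is there a pre-dose baseline?** The plan gives no expected adverse event rate and no power figure for safety, so there is nothing to reproduce. The first check is a reading of the text.

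1. Events are rated in the weekly survey (6.2.3), and that survey starts at Week 1 (6.3). No adverse event or symptom checklist is listed at Week 0.
2. Screening collects medical and psychiatric history and comorbidities (5.1, 6.3). The protocol describes the PHQ-9, given at Week 0 and bi-weekly, as assessing depression with an item on suicidal ideation. No Week 0 measure is described as covering nausea, headache or unusual dreams. The baseline is partial.
3. Section 6.3.2 starts the weekly surveys the day after the Day 0 call, while drug is shipped at Week 1 (6.1.3) and started on receipt (6.3). For some participants the first survey may precede the first dose, but nothing guarantees it. With no defined starting point, a complaint reported then could itself be counted as emergent.

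**How large could the effect be?** Inputs from the plan: "We plan to enroll 40 participants across two sites", with twenty randomized to varenicline (5.1), hence 20 per arm. Assumptions, none given in the documents:

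- true emergent rates e of 30% (placebo) and 60% (varenicline);
- a share b of participants who have a pre-existing complaint, report it and have it counted, equal in both arms and independent of true emergent events;
- two-sided alpha of 0.05, since Section 6.4.2 states none.

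Observed rate = b + (1 − b) × e.

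Observed risk difference = (1 − b) × (true risk difference).

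At b = 0.20:

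- placebo: 0.20 + 0.80 × 0.30 = 0.44
- varenicline: 0.20 + 0.80 × 0.60 = 0.68
- difference: 0.80 × 0.30 = 0.24
- ratio: 0.68 / 0.44 = 1.55

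| b | Placebo | Varenicline | Risk difference | Risk ratio | Exact Fisher power |
|---|---|---|---|---|---|
| 0 | 30% | 60% | 0.30 | 2.00 | 0.35 |
| 10% | 37% | 64% | 0.27 | 1.73 | 0.27 |
| 20% | 44% | 68% | 0.24 | 1.55 | 0.22 |
| 30% | 51% | 72% | 0.21 | 1.41 | 0.19 |
| 50% | 65% | 80% | 0.15 | 1.23 | 0.12 |

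With other assumed true rates the pattern is the same. At b = 20%, 20% vs 50% becomes 36% vs 60% (Fisher power 0.41 to 0.21), 30% vs 70% becomes 44% vs 76% (0.60 to 0.43), and 40% vs 80% becomes 52% vs 84% (0.65 to 0.49).

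The factor (1 − b) does not depend on the assumed event rates. The size of b is unknown.

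**The case against.** The strongest reply is that adverse event capture is scheduled. Section 6.2.3 places it in the weekly assessments, which have a row in Section 6.3.5 and recur in the list for Weeks 1 to 12. The assessment that Section 6.2.1 says lies below is plausibly Section 6.2.3 itself. This stands: a reader might infer from the missing adverse event row that events go uncollected, and the documents do not support that. What is missing is a named row, timing for any separate survey, and anything at Week 0.

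A second reply is that pre-existing symptoms can be identified from screening history, the Week 0 PHQ-9 and staff judgement of relatedness. This stands in part, so it would be too strong to say that separation is impossible. But none of these is linked to the analysis in Section 6.4.2, formal attribution coding leaves out mild and moderate events, and the analysis counts emergent events, not related ones.

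Third, nothing in Section 6.4.2 says that pre-existing symptoms will be counted, this is a 40-person pilot aimed at abstinence effect sizes, and power is only 0.35 in the illustration even with perfect classification. All of that is fair. The power figures are therefore secondary; the lasting harm would be to the reported rates and their difference.

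Two further inferences fail. The WSWS2-B is not the only measure of withdrawal: both e-cigarette dependence measures in Section 6.2.1 cover it at Weeks 0 and 8. Nor is it an error that symptoms caused by quitting enter the comparison, because in a randomized comparison of the total effect of assignment they are among its consequences.

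**Conclusion.** The point holds in a limited form. Section 6.4.2 rests on an undefined term, and the plan takes no symptom checklist before the first dose that would let anyone apply a definition to common complaints. If pre-existing complaints are reported and counted, both arms' rates are inflated and the risk difference is multiplied by (1 − b): a loss of one fifth at b = 20% and one half at b = 50%. Those values of b, and the event rates in the illustration, are assumptions. The calculation also takes b to be equal in the two arms, which randomization gives in expectation. A reader might infer that the safety comparison is biased toward one arm, or certain to be diluted. The documents support neither: the effect is attenuation, and it depends on how events are counted.

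The missing time point for the WSWS2-B is a separate scheduling omission. It shows in two places (no week in Section 6.2.1, an empty row in Section 6.3.5), so a mark lost when the table was read is an unlikely explanation.

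**What to change.** 1. Give one symptom checklist with mild/moderate/severe ratings at Week 0, before drug is mailed, and the same checklist in the weekly surveys already used for adverse events.
2. Add a row for it in Section 6.3.5, and make Sections 5.1, 6.2.1 and 6.2.3 refer to that one instrument.
3. In Section 6.4.2, define an event as study emergent only if it occurs after the first dose and is new or rated worse than at Week 0. This needs a first-dose date, which the daily pill counts in the weekly survey could supply.
4. Give the WSWS2-B explicit weeks, including Week 0, in both Sections 6.2.1 and 6.3.5.

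The cost is small: a short checklist at an intake that is already paid, some added items on existing REDCap surveys, and a minor amendment. The downside is a slightly longer intake and slightly longer surveys. The change helps only participants not yet dosed; for anyone already on drug, the missing baseline should be acknowledged in the report.

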2.1.2 Clinical Experience

We are using the same dose of the oral medication for vapers as we would for cigarette smokers. The participants will be given a dose titrated to 2mg daily which co aligns with the current FDA approved dose for smoking cessation.

Black-box warnings were removed by the FDA in recent years following the large clinical EAGLES trial showing that this is a low risk medication.¹ Additionally, meta-analyses have been conducted that show varenicline as a safe and useful medication.¹⁷⁻²⁰ Some side effects of varenicline include nausea, constipation, indigestion, abdominal pain, heartburn, increased or decreased appetite, trouble falling asleep or staying asleep, unusual dreams or nightmares, headache, lack of energy, back, joint, or muscle pain, and abnormal menstrual cycles.

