Pharmacotherapy: Twenty participants will be randomized to receive active varenicline. Prior to randomization, the study physician, [name] or nurse practitioners from the Tobacco Treatment Service/PI [name] will conduct a pre-randomization medical review to ensure that they qualify for varenicline based on study eligibility criteria collected during primary (e.g., smoking history, age, medical history, and comorbidities) and secondary screening (psychiatric history, suicidal history, pregnancy status). A summary report that we create within our REDCap screening database, will be delivered electronically to study physician/nurse practitioners/PI [name]. They will review each participant's information and will determine whether to 1) accept the individual into the study, 2) reject the individual into the study (i.e., not eligible for varenicline), or 3) ascertain more information from the individual before either the decision to accept/reject the participant. The study physician/nurse practitioners may contact the individual to engage in further clinical interviewing of the potential participant. The disposition of each participant will be tracked within this screening database, allowing us to complete all CONSORT steps to study flow. The individual will not proceed to randomization and intake until we have signed, explicit documentation from the study physician/nurse practitioners/ PI [name] to do so. Thus, these procedures ensure that we retain physician/APRN oversight and approval of varenicline disbursement at the study outset. [name]/APRNs from the Tobacco Treatment Service retains their role in evaluation of adverse events as noted elsewhere within this application.

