6.2 Assessments

6.2.1 Efficacy

Study Assessments

The following tools will be used for the assessments conducted at baseline (week 0) and end of follow-up (Week 0, 8 & 12).

Demographics (Week 0): This questionnaire will collect basic demographic information for each subject including gender, ethnicity/race, employment status, etc.

Smoking/Tobacco Use History (Week 0): This will collect basic info about smoking and smoking cessation history, prior varenicline use, e-cigarette history, tobacco and nicotine product flavor preference, etc.

Modified Questionnaire on Smoking Urges (QSU) (Week 0, 8 & 12): This 3-item assessment is used to examine smoking related urges such as desire to smoke, anticipation of immediate positive outcome, etc.³¹E-cigarette Dependence (Week 0 & 8): The NIH Patient-Reported Outcomes Measurement Information System (PROMIS) measure for daily smokers has also been adapted to measure for use of other tobacco products.^{30, 40} This is a 4-item e-cigarette dependence questionnaire that measures withdrawal and craving.

E-cigarette Dependence Index (Week 0 & 8): This is a 10-item e-cigarette dependence questionnaire that measures difficulty quitting, withdrawal and cravings.⁵⁷

Subjective Effects Cigarettes and E-cigarettes (Week 0, Week 4): Participants will report on subjective evaluation about cigarettes and e-cigarettes. Subjective evaluation includes items derived from the Modified E-Cigarette Evaluation Questionnaire (meCEQ)⁵⁸ that have also been adapted for alternate tobacco products. It measures the degree to which participants experience reinforcing effects from smoking and e-cigarettes. The scale yields five clusters or domains: Smoking Satisfaction, Psychological Reward, Aversion, Enjoyment of Respiratory Tract Sensations, and Craving Reduction.⁵⁶

Patient Health Questionnaire-9 (PHQ9) (Week 0 and Bi-Weekly): which assesses for depression and includes an item on suicidal ideation.⁵⁰

Wisconsin Withdrawal Scale Brief (WSWS2-B): This 6-item scale assesses current symptoms of nicotine withdrawal including cravings and irritability.⁵⁹

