6.2.3 Adverse Events Definition and Reporting

Adverse Events:

Participants will have the phone numbers of the Co-PIs, [name] [contact]) and [name] [contact]) and will be prompted to contact them if an adverse event occurs, along with the previously mentioned adverse event procedures. If a participant contacts the research team due to an adverse event, the event will be appropriately addressed, and the event will be reported per the criteria below. Adverse events will also be tracked via weekly assessments, where they will be able to rate the incident as mild, moderate, or severe. The research staff, with the guidance of [name] (for MUSC) and [name] (for Yale), will track the relatedness of the incident to study medication. The variables that we will encourage the pharmacist/APRN to assess include severe renal impairment, history of serious hypersensitivity or skin reactions to varenicline, an immediate (within 2 weeks) post myocardial infarction period, serious arrhythmias, unstable angina pectoris, or hemodynamically or electrical instability. We will determine if any adverse events result in dropouts or are serious according to FDA guidelines.

Serious adverse events, whether unanticipated or anticipated, will be reported immediately (within 24 hours) to the MUSC or Yale Institutional Review Board. The PIs will evaluate the adverse event and determine whether the adverse event affects the Risk/Benefit ratio of the study and whether modifications to the protocol or the consent procedures are required.

Plans for reviewing and reporting non-serious anticipated or unanticipated adverse events: Any participants' experiences of anticipated and unanticipated adverse events will be reported on an annual basis to the MUSC Institutional Review Board.

Plan for grading adverse events. Serious Adverse Events (SAE). The FDA's definition of serious adverse events (21 CFR 312) will be used. Serious Adverse Events include any untoward medical occurrence that at any dose results in death or the immediate risk of death, hospitalization, or the prolonging of an existing hospitalization, persistent or significant disability/incapacity or a congenital anomaly/birth defect, new cancer, or medication overdose. Adverse events will be defined and graded for risk as follows:

Coding of Severity:

- 0 = No adverse event or within normal limits
- 1 = Mild adverse event
- 2 = Moderate adverse event
- 3 = Severe, resulting in psychiatric or medical hospitalization

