6.3.1 Study Schedule

1. Intake Procedures (Week 0): Before joining the study, the patient will have first completed a screening visit using a telehealth platform (i.e., Doxy.me, Zoom, or other HIPAA compliant tele-video conferencing software) to obtain their consent using an electronic REDCap consent form) to confirm their eligibility. This research study will use exclusively remote/telehealth procedures as detailed below.

Once the informed consent has been signed, the research staff will ask a few additional questions to determine final eligibility. If they are a female of the age 55 or below, we will send them a pregnancy test in the mail. They will take the at home pregnancy test and complete a secure online survey to verify their test results. After final eligibility has been confirmed, they will be asked to complete some questions about their e-cigarette use.

Randomization (Week 0): They will be randomly assigned, like a flip of a coin, to either the (a) active varenicline medication group, or (b) the placebo group. Neither they nor research staff will know what medication condition to which they have been assigned; only the study pharmacists who prepare and mail their medication will know their medication condition assignment.

Treatment Phase (Week 0-Week 8): They will be sent an 8-week supply of the medication or placebo, along with a guided self-change booklet with information regarding quitting vaping. The study medication will be mailed to them free of charge. Neither they nor your doctor will decide which group they are in. Upon receipt of medication, they will receive a call from our tobacco treatment specialist. This will be a brief orientation call during which the specialist will go over medication use instructions with them. All participants will be encouraged to start their medication as soon as they receive it and to set a quit date 1-2 weeks after receiving the medication.

End of Follow up Phase (Week 12): End of treatment assessments will be completed at week 12.

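### The only between-arm safety analysis in the statistical plan is a test on the share of participants with adverse events, without an estimate or interval, and the PHQ-9 is not compared between arms

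*Combined protocol and SAP*

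**What the plan says.** Section 6.4.2 sets out the safety analysis in two sentences. Events are collected during the treatment phase, and then: "The proportion of participants reporting study emergent adverse events will be compared between groups using a Chi-Square test", or Fisher's exact test where that is appropriate. It gives no effect measure, interval or significance level. It does not mention event type, severity, seriousness or discontinuation.

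Section 6.4.1 treats efficacy differently. It promises risk ratios with 95% confidence intervals for abstinence and for vaping days, and says the results will serve to design and power a follow-up trial.

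The data for more than this are collected. Under section 6.2.3, "Adverse events will also be tracked via weekly assessments", with participants rating each as mild, moderate or severe. The same section has a 0-5 grade, attribution from grade 3 upwards, and a determination of which events are serious or lead to dropout. Section 2.1.2 names the expected effects: "Some side effects of varenicline include nausea, constipation, indigestion" and others, including disturbed sleep and unusual dreams. Section 6.2.1 lists "Patient Health Questionnaire-9 (PHQ9) (Week 0 and Bi-Weekly): which assesses for depression", including an item on suicidal ideation. Nothing in section 6.4 uses that instrument.

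On size, section 5.3.1 states "We plan to enroll 40 participants across two sites" and section 5.1 states "Twenty participants will be randomized to receive active varenicline".

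**The concern.** A p-value on one composite proportion answers only whether the arms differ detectably in the share with any event. In a 40-person pilot the useful question is how large an excess the data are compatible with, and for which events. A test result cannot answer that.

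The composite also gives a mild headache the same weight as a severe mood change, so a difference in one of the named effects can be diluted. The PHQ-9 is measured repeatedly in both arms, and the protocol gives suicidality much attention, yet as planned those scores would serve individual alerts and not a comparison of the arms.

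Two things are at stake. A non-significant result could be taken as similar safety when the data allow a substantial excess. And the follow-up trial would inherit effect sizes for abstinence but none for harm.

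**Working it through.** The documents state no power, event rate or sample-size derivation for safety, so there is no figure of the plan's own to reproduce.

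**Inputs from the documents.** 40 participants (5.3.1), 20 of them on varenicline (5.1), hence 20 vs 20. Chi-Square, or Fisher when appropriate (6.4.2).

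**Assumptions.** Two-sided level 0.05. Event rates are illustrative. No dropout, except where stated. The plan does not say when Fisher is appropriate, so two readings are shown: Fisher always, and Chi-Square (uncorrected) with Fisher when the smallest expected count, min(x+y, 40−x−y)/2, is below 5.

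**Power.** Exact enumeration over all tables with x events on varenicline and y on placebo:

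power = Σₓ Σᵧ Bin(x; 20, p₁) · Bin(y; 20, p₀) · 1{p-value(x, y) ≤ 0.05}

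| Varenicline vs placebo | Gap (points) | Fisher always | Chi-Square/Fisher rule |
|---|---|---|---|
| 30% vs 10% | 20 | 24% | 29% |
| 60% vs 40% | 20 | 14% | 22% |
| 40% vs 10% | 30 | 49% | 59% |
| 60% vs 30% | 30 | 35% | 46% |
| 50% vs 10% | 40 | 74% | 83% |
| 60% vs 10% | 50 | 91% | 95% |

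With an assumed 20% dropout (16 per arm), the figures for 30% vs 10% fall to 17% and 18%, and for 60% vs 40% to 12% and 21%.

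**What the test says and what an interval would say (illustrative counts).**

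- 6/20 vs 2/20. The smallest expected count is (6+2)/2 = 4, so Fisher applies: p = 0.24. The risk difference is 0.30 − 0.10 = 0.20. The Wilson limits are 0.145 to 0.519 and 0.028 to 0.301. Newcombe lower limit: 0.20 − √[(0.300−0.145)² + (0.301−0.100)²] = −0.05. Upper limit: 0.20 + √[(0.519−0.300)² + (0.100−0.028)²] = 0.43. The test says non-significant; the interval says anything from 5 points fewer to 43 points more.
- 14/20 vs 8/20. The difference is 30 points (95% CI −1 to +54), Chi-Square p = 0.057.
- 10/20 vs 10/20. The difference is 0 (−28 to +28). Even identical proportions do not exclude a 25-point excess.
- 8/20 vs 2/20. The smallest expected count is 5, so Chi-Square applies. The pooled proportion is 0.25 and the statistic is 0.30²/(0.25 × 0.75 × 2/20) = 4.80, p = 0.028. Fisher on the same table gives p = 0.065. The conclusion here depends on a choice that the plan leaves open.

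**PHQ-9.** A simple two-sample comparison at 20 per arm has 80% power for about 0.89 SD and 35% power for 0.5 SD. It too is of use as an estimate with an interval, not as a test.

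**The case against.** Safety is not left to one test. Section 7.11 has the principal investigator review event frequency overall and by arm at least every six months. Section 6.2.3 provides grading, attribution and reporting of serious events within 24 hours. Sections 3.2.1 and 7.12 act on individual PHQ-9 scores through flags monitored daily. This stands: a reader who infers that the protocol judges safety only by a significance test goes too far. These are monitoring steps, however, and none commits the trial to a reported between-arm estimate.

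A reader might also infer that 20 per arm cannot inform safety, or that a non-significant result is nearly certain. The table shows otherwise: 50% vs 10% is detected in 74-83% of trials. Nor do the documents say that a non-significant result will be read as no difference. That is a risk of misreading and not a stated intention.

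It is also tempting to argue that weekly questioning pushes the any-event share towards 100% in both arms. If 20-30% report an event each week, independently, then 1 − 0.8⁸ = 83% to 1 − 0.7⁸ = 94% report one over eight weeks. But neither the weekly rate nor independence is in the documents. At 5-10% per week the same formula gives 34-57%, and events that recur in the same people lower the share further. The ceiling is possible but not established.

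Finally, section 6.4.2 does not forbid tables by type or severity, and low power is normal in a pilot whose stated purpose is efficacy and effect sizes for abstinence. Both are fair. The first leaves the tables uncommitted. The second is the reason to estimate, and no reason to enlarge the trial.

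**Conclusion.** The concern holds for the statistical plan. Section 6.4.2 commits to a test with no estimate or interval and no stated breakdown, and section 6.4 does not compare the PHQ-9 between arms. At 20 per arm, true excesses of 20 to 30 points in the scenarios above would be non-significant in roughly 41% to 86% of trials (100% minus powers of 59% to 14%), depending on the placebo rate and on which test is used.

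These figures rest on an assumed two-sided 0.05 level, illustrative event rates and complete follow-up. Dropout would lower the power.

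The consequence is limited: a p-value that could be misread as similar safety, and no harm estimate for the next trial. It does not follow that safety goes unmonitored or that large harms would usually be missed. This is a cheap improvement in analysis and reporting that should be made; it is not a flaw in the design.

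**What to change.** In section 6.4.2:

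- Report n (%) by arm with the risk difference and a 95% confidence interval (for example Newcombe) for any event, each listed event type, worst severity, seriousness and event-related discontinuation. Label these descriptive.
- The test may stay for the any-event proportion. If it does, state when Fisher replaces Chi-Square.
- Add the between-arm difference in post-baseline PHQ-9 total, adjusted for the Week 0 score, with a 95% confidence interval.
- Add the number per arm with any post-baseline item 9 score above 0.

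No further participants, visits or instruments are needed. The cost is revised wording and a few more tables. With many event types some intervals will exclude zero by chance, which is why they should be labelled descriptive. The PHQ-9 interval will be wide at this size.
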